2.2 ENDPOINTS

2.2.1 Primary Endpoint

Feasibility of Phase III trial, i.e. that eligible patients can be identified correctly, in sufficient numbers, enrolled and >95% retained in follow-up at one year, to achieve feasibility target sample size recruitment and randomisation of 400 patients in 24 months in the UK.

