SUPPLEMENT – LACunar Intervention Trial 2 (LACI-2) Statistical Analysis Plan

SECTION 1. ADMINISTRATIVE INFORMATION

1 Title and trial registration

1a Title: Lacunar Intervention Trial 2

Acronym: LACI-2

1b Registration: ISRCTN14911850; IRAS project number: 206480

2 SAP version: 1.5 (06 June 2022)

3 Protocol version: 7.0 (14 October 2020)

4 SAP revisions

4a Revision history:

Version 1.4 to 1.5

- Text added about the planned soft database lock and analysis (section 13a).
- Text added explaining comparison of dual versus no treatment (section 27a).
- Differences and p values removed (Tables 1, 5).
- Analyses comparing dual versus no treatment do not include all four groups so cilostazol only and ISMN groups removed (Table 9).

4b Justification for each revision: N/A

4c Timing of SAP revisions: These antedate data lock and analysis. Where there is a difference between the protocol (on website), published protocol ¹ and SAP, the SAP will take precedence.

5 Roles and responsibilities

Author: [name]

Responsible statisticians: [name] (blinded statistician), [name] (blinded statistician), [name]

Chief Investigator: [name]

Contributors and roles:

[name], [name], [name], [name], [name], [name], [name], for the LACI-2 Investigators*

6 Signatures

Role	Name	Signature	Date
6a Author:	[name]	 [name] (Jun 9, 2022 10:02 GMT+1)	Jun 9, 2022
6b Senior statistician	[name]		Jun 15, 2022
6c Chief Investigator:	[name]		Jun 9, 2022

SECTION 2. INTRODUCTION

7 Background and rationale

Prior to analysis and presentation of the primary results, this publication presents the statistical analysis plan (SAP)^{2 3} alongside the detailed listing of baseline characteristics presented in the accompanying baseline paper. This Supporting Information Appendix S1 details the full SAP and is presented prior to locking of the study database so that analyses are not data driven or reported selectively.⁴ In addition to the SAP, we also list planned secondary analyses and substudies. The SAP follows the recommended layout.^{2 3}

8 Objectives

8a Primary Objective: To determine whether a prospective, randomised trial of cilostazol and ISMN, individually or in combination, on a background of guideline stroke prevention therapy, in lacunar ischaemic stroke is feasible in the UK, thence proceeding as seamlessly as possible to a large phase III trial.

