- Recruitment of sufficient patients, i.e. 400 patients in 24 months in the UK (and taking account of interruption due to COVID-19).
- >95% of randomised patients are retained for follow-up at one year.

Secondary outcomes - participant

Tolerability: 75% of patients will be able to tolerate trial medication, in at least half dose, up to one year after randomisation (i.e. less than 25% will stop trial medication completely through inability to tolerate the drugs).

Safety

- Symptoms of systemic or intracranial bleeding.
- The absolute risk of death, including fatal haemorrhage, does not differ significantly, i.e. fall outside the upper 95% CI of 2% per year on trial drugs versus no trial drugs, when given in addition to guideline stroke prevention drugs.
- There are no new ischaemic or haemorrhagic brain lesions or increase in SVD lesions on one year MRI significantly (at the p<0.01 level).

Efficacy

- Individual event-rates for stroke, TIA, myocardial ischaemia, cognitive impairment and dementia.
- The *combined rate* of recurrent stroke, MI, death, mild cognitive impairment (including dementia), dependency and new stroke lesions on scanning at 1 year will be 40-50% at one year after enrolment in order to allow detection of a modest but clinically-important reduction in poor outcomes in a phase III trial.
- Health economic measures include the health utility score (EQ-5D-5L) and the visual analogue score (EQVAS) at 12 months.

26b Units: Units will be shown in tables.

26c Calculations/transformations: Quality of life using UK weightings.

Brain frailty

Based on neuroimaging:

- Brain frailty = Atrophy + WML + Previous stroke lesion ⁷

- SVD score for CT = WML, lacunes; for MRI includes WMH, lacunes, PVS and microbleeds ¹⁵

Montreal cognitive assessment-modified (MoCA-m) trails

Since Trails A and B are performed, the MoCA trail is not collected but rather estimated from the Trails B score:

- If Trails B score <12 then MoCA trail = 0
- If Trails B score >=12 then MoCA trail = 1

27 Analysis methods

27a Methods

Primary endpoint

- Tabulation and graphical presentation of participant recruitment aiming for 400 participants in 24 months.
- Tabulation of retention of participants at one year aiming for >95%.

Analyses of secondary outcomes

Tabulations of:

- Tolerability to trial medications aiming for 75% of patients taking at least half dose for up to one year after randomisation.

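### SAP Table 2 scores the primary recruitment endpoint as 363/400 with no time limit, and the COVID-19 allowance in SAP 26a is not quantified

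*SAP*

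**What the plan says.** Protocol 2.2.1 makes feasibility the primary endpoint and includes "recruitment and randomisation of 400 patients in 24 months in the UK", together with retention at one year. In the protocol text supplied, that section has no COVID-19 clause.

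The SAP states the recruitment part in three places, in three forms:

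- Section 26a gives "400 patients in 24 months in the UK (and taking account of interruption due to COVID-19". It attaches no dates and no start of clock, and it does not say whether the period is extended or the target reduced.
- Section 27a plans "Tabulation and graphical presentation of participant recruitment aiming for 400 participants in 24 months". The 24 months remain; the allowance is absent.
- Table 2 gives a recruitment metric of 400 patients with no period in the row label or the metric. Its result cell is filled with 363/400 (90.8%), while the other results are placeholders. The retention row just below keeps its one-year time point.

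The second part of the endpoint, ">95% of randomised patients are retained for follow-up at one year", is consistent across the SAP and is not affected.

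SAP section 4c gives the SAP precedence over the protocol where they differ, and says of the revisions: "These antedate data lock and analysis". The list of changes from version 1.4 to 1.5 does not mention the COVID-19 wording. SAP section 7, under confounding covariates, says that recruitment will be tabulated. No rule for met or not met is given.

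**The concern.** Recruitment in a fixed period is half of the trial's primary answer, and the primary objective is to show that the trial is feasible before a large phase III trial. A feasibility target of this kind is about pace. Table 2 removes the time element, so a reader of the results table would see about 91% of target whether recruitment took two years or four.

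The allowance in 26a compounds this. It overrides the protocol by the precedence rule, disagrees with 27a, and has no content that an analyst could apply. It stands in a SAP version that already prints the count, so any rule for applying it that is fixed from now on is fixed with the count in view. Database lock gives no protection on this item.

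At stake are the reported primary result and the accrual rate carried into phase III planning. No screening logs are kept (Protocol 5.4, SAP section 21), so the yield from eligible to randomised patients cannot be recovered from them. That leaves the recruitment rate as the main evidence on accrual.

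**Working it through.** **Inputs.** Target of 400 in 24 months (Protocol 2.2.1; SAP 26a and 27a). Randomised: 363 (SAP Table 2), taken here as the final total. Planned phase III size: 1100 (Protocol Table 7, model D; SAP 11b). Recruitment dates and length of interruption: not in the documents, so countable time is varied as an assumption.

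**Step 1: the plan's own figure.** 363/400 = 90.75%, which rounds to the printed 90.8%. The shortfall is 400 − 363 = 37 patients, or 9.25%.

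**Step 2: the count criterion.** The number randomised by month 24 cannot exceed the total of 363, and 363 < 400. Lengthening the period or removing pause months from it does not add patients. If only the clock is adjusted, the target is missed for any adjustment.

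**Step 3: the implied rate.** 400/24 = 16.67 per month. Countable time at which 363 patients equal that rate: 363/16.67 = 21.8 months.

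**Step 4: range over countable time.** Rate = 363/months; pro-rata target = 16.67 × months.

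| Countable months (assumed) | Rate per month | Pro-rata target | 363 as % of it | Table 2 prints |
|---|---|---|---|---|
| 18 | 20.2 | 300 | 121.0% | 90.8% |
| 21 | 17.3 | 350 | 103.7% | 90.8% |
| 24 | 15.1 | 400 | 90.8% | 90.8% |
| 30 | 12.1 | 500 | 72.6% | 90.8% |
| 36 | 10.1 | 600 | 60.5% | 90.8% |
| 48 | 7.6 | 800 | 45.4% | 90.8% |

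The printed figure equals performance against the stated pace only if countable time is exactly 24 months.

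**Step 5: consequence for phase III.** At unchanged site capacity, 1100 patients would take 1100/16.67 = 66 months at the target rate, 1100/10.08 = about 109 months at the 36-month rate, and 1100/7.56 = about 145 months at the 48-month rate. A count without time cannot separate these.

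**The case against.** The case for leaving the plan alone has real substance. Table 2 is a results shell with shortened metrics; its death row, for example, abbreviates a longer criterion in 26a. The endpoint is defined in 26a and analysed under 27a, and both keep the 24 months. The graph planned in 27a would be expected to show where recruitment stood at month 24. The shortfall is not hidden, since 90.8% is printed. Neither document states a monthly rate, so 16.7 is derived and the 21.8-month break-even belongs to a rate or pro-rata reading. Progression to phase III is described as resting on sufficient confidence and further funding (Protocol 1.2), not on a mechanical gate.

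Most of this stands, and it rules out three stronger readings that a reader might infer:

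- *The criterion has lost its time limit.* It has not. Only the Table 2 row omits it.
- *The COVID-19 allowance was added after the count was known.* The documents do not show this. The wording and the count appear together in version 1.5, but the log of changes from 1.4 does not list the wording, and no earlier history is given. It may predate the count.
- *The feasibility verdict can be set either way.* Under a time-only allowance, 363 stays below 400. A pass would need a pro-rata or rate reading, or a loose view of what counts as enough patients. The SAP does not exclude those readings, but it does not adopt them either. The retention criterion is untouched in any case.

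What does not stand is that 27a cures the problem. A graph does not correct the table cell that reports the primary result, and 27a and 26a disagree on the allowance.

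**Conclusion.** The point holds in limited form. Table 2 does not measure the stated primary recruitment endpoint: its 90.8% is a share of 400 with no period attached, while the protocol and SAP 26a and 27a all define 400 in 24 months. The allowance in 26a is unquantified and is absent from 27a and from the protocol section.

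Taking 363 as the final total, the endpoint of 400 is missed whatever time is excluded. What remains open is by how much the pace fell short, or whether it did: from above target at 21 countable months (103.7%) to well under half of it at 48 (45.4%). That range is assumption, because recruitment dates and suspension dates are not in the documents. When the COVID-19 wording entered the SAP is also not shown. The severity is should-fix: the change is nearly free, and it bears on the reported primary result and on the accrual rate taken into phase III.

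**What to change.** Align SAP 26a, 27a and Table 2 before final lock:

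1. Change the Table 2 recruitment metric to 400 in 24 months. Report first, unadjusted, the number randomised by month 24 against 400, as met or not met, and state the date from which the 24 months run.
2. Beneath it, as a line labelled supportive, give the total randomised, the actual recruitment months, and the rate per open month with and without the documented COVID-19 suspension, against 16.7 per month. Fix the start and end dates of the suspension before final lock.
3. In 26a, define the allowance by those dates and state that it affects only the clock and not the target of 400. Use the same wording in 27a.
4. Record in the revision history when the COVID-19 wording was introduced.

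A rate per open site-month would help phase III planning but is optional. The protocol already joins recruitment and retention, so a sentence requiring both is not essential.

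The cost is some SAP wording and a few table rows built from randomisation dates already held. The downside is that the unadjusted primary recruitment result will read as missed.

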2.2.2 Secondary Endpoints

Tolerability - 75% of patients will be able to tolerate trial medication, in at least half dose, up to one year after randomisation (i.e. less than 25% will stop trial medication completely through inability to tolerate the drugs).

Safety - symptoms of systemic or intracranial bleeding, recurrent cerebral and systemic vascular events, and vascular and non-vascular causes of death will be collected. The absolute risk of death, including fatal haemorrhage, will not differ significantly (ie fall outside the upper 95% CI) from 2% per year on trial drugs versus no trial drugs, when given in addition to guideline drugs; and will not increase bleeding or ischaemic SVD lesions significantly (at the p<0.01 level) on MRI.

Efficacy – individual event-rate data (stroke, TIA, myocardial ischaemia, cognitive impairment and dementia, will be collected. The *combined rate* of recurrent stroke, MI, death, cognitive impairment and dependency will be 40-50% at one year after enrolment in order to detect modest but clinically-important reductions in poor outcomes.

Health Economics – data to assess health economic impact will be gathered.

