5.5 RANDOMISATION

5.5.1 Randomisation Procedures

The electronic randomisation system and trial database are hosted by the University of Nottingham. Randomisation involves minimisation on key prognostic factors including: age, sex, stroke severity (NIHSS), dependency resulting from the stroke, systolic blood pressure $\leq/ > 140$, smoker status, time after stroke, years of education. Years of education give an estimate of pre-morbid cognitive ability and predicts post-stroke cognitive impairment; BP and smoking predict recurrent stroke; delay since stroke reflects disease activity; age, sex and stroke severity are standard minimisation variables. This approach ensures concealment of allocation (note allocation concealment means that it is not possible to guess which treatment the next patient will be randomised to), minimises differences in key baseline prognostic variables, and improves statistical power. Randomisation will not be minimised by Centre because this may result in high rates of allocation prediction, but a pre-specified post-hoc analysis by centre will be performed to investigate and adjust for heterogeneity of treatment effect by centre.

Randomisation will allocate a trial treatment, which will be prepared by the local participating Pharmacy.

Note that randomisation will be performed during normal office hours (09.00 – 17.00) and the trial allows for randomisation to occur months or years after the stroke. Therefore, in the event of computer failure (for example: server failure), the investigator will wait until the computer system is re-established to perform the randomisation. Normally, this would only be a few minutes to two hours. However, if this delay requires the patient to return on a separate occasion to collect the drugs, then a separate appointment will be made and the patient's travel expenses covered as per other trial visits.

Patients will be randomised to one of the following at a 1:1 ratio as per Section 6.2:

- cilostazol versus no cilostazol
- isosorbide mononitrate versus no isosorbide mononitrate

resulting in a partial factorial comparison of cilostazol versus isosorbide mononitrate versus both drugs versus neither drug.

The randomisation algorithm will allocate a unique identifier which will be used to label the treatment pack containing the appropriate drug made up for the patient and dispensed by the local Pharmacy.

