9 STATISTICS AND DATA ANALYSIS

9.1 SAMPLE SIZE CALCULATION

There are few data on which to base sample size. There is little experience with cilostazol in Europe or North America, and little experience with ISMN in this group of patients in the UK (or in any patients with stroke). We have been guided by colleagues in Japan where cilostazol is in common use and there is experience with it in stroke. The main purposes of the trial are to assess tolerability and safety.

Table 6 Annual absolute risks (%) of outcome events after lacunar stroke

Vascular death	Non-vasc death	Non-fatal isch stroke or TIA	Non-fatal ICH	MI	MACE	Dependent (mRS 3-5)	Any cogn impt.	Dementia
1.8	0.5	2.5	0.5	0.6	3	15	30	15

We calculated mean annual event rates (Table 6) from trials (SPS3,³³ lacunar patients in ENOS⁵⁰ IST-3,⁶³ of cilostazol, Figure 1) and observational data (LADIS;⁶⁴ our^{4, 65} and other⁶⁶

studies). We expect deaths including vascular deaths of median 2.0% p.a., with 4% being the upper 95% CI of 2% in 400 patients.³³ LACI-2 therefore has a sample size of 400.

For a main Phase III trial, recurrent stroke 2.5%pa, MI 0.6%pa and vascular death 1.8%pa,^{4, 33} (MACE) are infrequent; new cognitive impairment c16% at one year,^{6, 66} dependency 15%, are frequent and important to patients, justifying their inclusion in a composite primary outcome. However, these event rates are imprecise with wide ranges; more precise estimates are needed. We estimate main Phase III trial sample size at 1100 (Table 7), assuming 80% power, alpha 5%, 10% loss to follow-up, composite event rate (45%) and conservative estimate of cilostazol effect (20% RRR is the lower 95% CI of effect, Figure 1). A primary outcome including MRI SVD progression (A, below) was considered but at least 15% of patients miss repeat MRI, sample sizes were similar (or larger, due to variance in WMH change⁶⁵ short term), the cost is much higher and the WMH intermediary measure is less relevant to patients.

Table 7. Sample size for composite outcome in main trial, estimated event rates.

Composite model	A	B	Ci	Cii	D
Composite outcome for Phase III includes:	MACE, dementia, non-vasc death, new MR signs	MACE, dementia, death	MACE, cog↓, dependency↓, death		MACE, cog imp, depend, all death
1-beta (power)	80%	80%	80%	80%	80%
Event rate, control, pa	50%	10%	30%	30%	45%
Relative risk reduction	20%	20%	20%	30%	20%
Event rate, active, pa	40%	8%	24%	21%	36%
Total sample size	950	6626	1784	778	976

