Haematology (full blood count) and Biochemistry (urea, electrolytes, creatinine) – most recent value obtained since time of index stroke is acceptable unless clinical reason to expect change		X ^s				
Blood pressure		X ^s				X ^s [‡]
Cognitive test: document years of education; Montreal Cognitive Assessment (MOCA)		X ^s				
Timed Trail Making Test B		X ^s				X ^s [‡]
Dispense trial medication ²		X ^s			X ^s	
Structured questionnaire: symptoms; medication history and IMP tablet adherence			X ^s	X ^s	X ^c	X ^c
Structured questionnaire: recurrent vascular events, mRS, TICS, t-MOCA, SIS, ZUNG					X ^c	X ^c
Obtain IQCODE (post/phone) from relative						X ^c
Follow-up brain MRI						X ^s
Health Economics data: EQ-5D-5L, EQ-VAS						X ^c
Adverse event / con meds reporting as necessary			X ^s	X ^s	X ^{s,c}	X ^{s,c}

[†] Consent will be obtained before the data collection procedures commence or randomisation is performed. Randomisation occurs at the end of the baseline visit.

[‡] at 12 months in some centres only.

² Dispensing in 3-monthly intervals is allowed.

^s Assessment performed by local site team.

^c Assessment performed by blinded assessor who is part of the central trial team.

SIS: Stroke Impact Scale; TICS: telephone interview for cognitive status; t-MOCA: telephone MOCA.

SECTION 4. STATISTICAL PRINCIPLES

Confidence and p values**16 Level of statistical significance**

The results of analyses and comparisons will be shown with $p < 0.05$.

17 Multiplicity

No adjustment will be made for multiplicity.

18 Levels of confidence intervals

The results of analyses and comparisons will be shown with 95% confidence intervals.

19 Adherence

19a Definition: 75% of patients will be able to tolerate trial medication, in at least half dose, up to one year after randomisation (i.e. less than 25% will stop trial medication completely through inability to tolerate the drugs).

19b Adherence presentation: See Table 4.

19c Protocol deviations: Protocol violations will be reported to the sponsor within 24 hours of becoming aware of the violation. Protocol deviations will be recorded in a protocol deviation log with these submitted to the sponsors every 3 months.

19d Protocol deviation presentation: Listing of violations and deviations and their frequency.

20 Analysis populations

Three populations are defined:

1. Intention-to-treat: All consented participants with a primary outcome measure.

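### MRI safety counts as met whenever an increase in lesions misses p<0.01, with no margin or power behind it, so the criterion can pass a result whose own 95% CI excludes no effect

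*SAP*

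**What the plan says.** The SAP's safety outcomes in item 26a include this MRI criterion: "There are no new ischaemic or haemorrhagic brain lesions or increase in SVD lesions on one year MRI significantly (at the p<0.01 level"). The sentence is awkward, but Protocol 2.2.2 makes the intent clear. The trial drugs "will not increase bleeding or ischaemic SVD lesions significantly (at the p<0.01 level) on MRI".

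The SAP's general rules differ. Item 16 sets the significance level at 0.05. Item 17 states: "No adjustment will be made for multiplicity". Item 18 states: "The results of analyses and comparisons will be shown with 95% confidence intervals".

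Item 27a compares MRI lesions between groups for cilostazol v none, ISMN v none, and both v neither, and does not repeat the 0.01. Table 9 lays out effect estimates with 95% CIs and p-values for all three. Neither document explains the 0.01, says whether it is one- or two-sided, or gives a margin, a power or an expected rate of new MRI lesions.

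**The concern.** There are two linked problems.

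- **Non-significance is read as safety.** Failing to show an increase is not evidence that there is none, least of all in a trial not sized for the question. The protocol bases the 400 participants on the precision of a 2% death rate, not on MRI lesions.
- **The lower level works the wrong way.** For an efficacy claim, 0.01 in place of 0.05 is cautious. For a harm test whose non-significance counts as reassurance, it is the opposite, because more real harms go unflagged. SAP 17 rules out reading 0.01 as a multiplicity correction.

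Together these let the SAP contradict itself. Any increase with two-sided p between 0.01 and 0.05 satisfies item 26a while the 95% CI required by item 18 excludes no effect. Protocol 2.1 says the MRI data will help give confidence that the drugs are safe enough to test in a large trial, so the wording of this conclusion matters.

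**Working it through.** **Is there a plan figure to reproduce?** None exists for this criterion. As a check on method, phase III model D (45% v 36%, 80% power, alpha 5%) was recomputed. The plain two-proportion formula gives n = [1.960√(2×0.405×0.595) + 0.842√(0.45×0.55 + 0.36×0.64)]² / 0.09² = 466 per arm, or 932 in total. With the Fleiss continuity correction it gives 488 per arm, or 976, which is the plan's figure.

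**Inputs**
- Recruited: 363 (SAP Table 2). Planned: 400 ("LACI-2 therefore has a sample size of 400").
- Allocation: 1:1 for each drug (Protocol 5.5.1).
- No repeat MRI: at least 15% (Protocol 9.1).
- Scanned per arm, single-drug comparisons: 363 × 0.85 / 2 ≈ 154. Both v neither: 363 × 0.85 / 4 ≈ 77.
- Control rate of new MRI lesions: not in the documents; assumed 5% to 20%.
- True effect: a doubling of risk, assumed for illustration.
- Test: two-sided (assumed), unadjusted, no continuity correction.

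**Power.** With d = p₂ − p₁ and p̄ the mean of the two rates:

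power = Φ{ [d − z√(2p̄(1−p̄)/n)] / √[(p₁(1−p₁) + p₂(1−p₂))/n] }, where z = 2.576 at 0.01 and 1.960 at 0.05.

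Example, 10% v 20%, n = 154, level 0.01: [0.10 − 2.576 × 0.0407] / 0.0403 = −0.12, so power is 45% and 55% are missed.

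**Share of true doublings missed**

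| Control rate | 154 per arm, p<0.01 | 154 per arm, p<0.05 | 77 per arm, p<0.01 |
|---|---|---|---|
| 5% | 82% | 62% | 92% |
| 10% | 55% | 31% | 80% |
| 15% | 28% | 11% | 64% |
| 20% | 10% | 3% | 45% |

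Simulation with 200,000 runs at 154 per arm gave power of 17%, 45%, 73% and 91% at 0.01, in line with the first column. With 170 per arm (400 × 0.85 / 2) the missed shares are 80%, 50%, 23% and 7%. With a one-sided 0.01 test at 154 per arm they are 75%, 45%, 20% and 6%.

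**Crossover.** More than half of true doublings are missed at p<0.01 only if the control rate is below about 10–11% (single drugs) or 17–19% (combination).

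**Smallest flagged increase.** From an observed 10% with 154 per arm, solve d = 2.576√(2p̄(1−p̄)/154) with p̄ = 0.10 + d/2. The answer is about 10.6 points (z = 2.58 at d = 0.106).

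**The internal contradiction in numbers.** Suppose 10% v 18.8% is observed. The pooled z is 0.088 / √(2 × 0.144 × 0.856 / 154) = 2.20, p = 0.028. The 95% CI is 8.8 ± 1.96 × 3.97 points, or 1.0 to 16.6. This meets item 26a, yet the interval excludes zero. It would also pass a one-sided 0.01 test (p = 0.014).

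**Beyond doublings.** At 154 per arm and p<0.01, power for a 10-point increase is 29% (20% v 30%), 23% (30% v 40%) and 21% (40% v 50%).

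**The case against.** The strongest reply is that the size rests on a lesion rate the documents do not give. That stands. A reader might infer that most true doublings would pass whatever the rate; this is not supported. For single drugs it fails above a control rate of about 10–11%, and power reaches 72% at 15% and 90% at 20%. The plan's sample-size table even hints at a high rate for MRI change broadly defined. Model A, which includes new MR signs, assumes 50%, against 10% for model B without them. That suggests roughly 40 points from MRI, although it is an inference and the models differ in other ways. At 40% v 60% with 154 per arm, power at 0.01 is 83%. Many Table 9 measures are ordinal or change scores, to which a doubling does not apply.

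A reader might also infer that MRI safety is a formal gate to phase III. The documents do not say so. The primary endpoint is recruitment and retention, Protocol 1.2 ties progression to confidence in procedures, event rates and recruitment, and SAP Table 2 has no MRI row. Nor do the SAP and protocol disagree, since both use 0.01.

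Finally, Table 9 will show readers 95% CIs, and the SAP itself calls the combination comparison very underpowered. This lessens the harm but does not remove it, because item 26a still judges safety by p<0.01 and not by the interval.

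**Conclusion.** The criterion is wrong as written. It turns a non-significant harm test into reassurance, at a level that makes harm harder to flag than the SAP's own 0.05, and it can conflict with the planned 95% CI. None of that depends on a lesion rate.

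The size does. The missed shares rest on an assumed control rate, a doubling of a binary outcome, 15% without MRI, a two-sided unadjusted test, and every participant entering both factors. Participants randomised to one drug only would make the arms smaller and the misses more frequent. Covariate adjustment, which the SAP plans, may change power somewhat. The problem is worst for less common lesions and for the combination.

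This is a secondary safety criterion that informs the phase III decision, and no more than that.

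**What to change.** Delete the p<0.01 criterion from SAP 26a and Protocol 2.2.2. In its place, for new infarct, new haemorrhage and SVD progression:

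- judge MRI safety by the 95% CIs already planned, in each of the three comparisons;
- add the absolute risk difference with its 95% CI for binary outcomes;
- state the upper confidence limit as the increase the trial has not excluded;
- do not describe a non-significant result as no increase.

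Replacing 0.01 with 0.05 would remove the clash with the CIs but not the main fault. At a 5% control rate with 154 per arm, 62% of doublings would still be missed. If a pass/fail rule is wanted, it needs a pre-stated margin for the upper limit, with the assumed lesion rate and power shown.

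The cost is a wording change in two documents and one extra estimate per binary outcome in Table 9. No new data are needed. The downside is a less favourable safety statement: if 10% were observed in both arms of 154, the 95% CI would be ±1.96 × √(2 × 0.10 × 0.90 / 154) = ±6.7 points, so the report would have to say that an increase of up to 6.7 points is not excluded.
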